The main risks to Famotidine which have been occurred in greater than or equal to 1% of subjects in clinical trials are: headache; dizziness; and constipation.

Other adverse reactions that were reported in less than 1 % of subjects in clinical trials include: fever, abnormal weakness or lack of energy; fatigue; heart palpitations; elevated liver enzymes; vomiting; nausea; abdominal discomfort; decreased appetite; dry mouth; decreased platelet counts in your blood; swelling of the tissue around your eyes; rash; eye redness and irritation; difficulty breathing; muscle pain; joint pain; seizure; hallucinations; depression; anxiety; decreased interest in sexual intercourse; difficulty falling asleep; prolonged sleeping; dry skin; flushing; ringing in your ears; altered sense of taste; and difficulty in men with achieving erections capable of intercourse. The following have also been reported during post-approval use of famotidine: changes to your heart by effecting the rhythm in which it beats; jaundice; inflammation and possible damage to your liver; decreased levels of white blood cells, red blood cells or platelets which could be life threatening; allergic reaction which could be life-threatening; rapid swelling of soft tissues often involving tissue around the face, limbs or genitals; hives; muscle damage; muscle cramps; confusion; agitation; tingling, numbness, or burning sensation in the skin often involving hands, feet, arms, or legs; pneumonia; and rash and blistering which could be life threatening.

In a recent prospective trial of patients with Parkinson's disease, doses of famotidine were escalated from 80 mg/day to 120 mg/day to 160 mg/day. No significant adverse effects were observed.¹⁵¹

11. Possible Reduction in Absorption of NAC due to increased Gastric pH

It is conceivable that due to the reduction in gastric pH that oral NAC may not be absorbed as effectively when given in combination. In order to mitigate this theoretical possibility, we have proposed a phase I trial of the combination of the two investigational drugs with twelve possible combinations described in greater detail below. Three arms are with NAC alone. Additionally, while the trial design should allow us to evaluate the possibility of a decreased effectiveness of NAC in combination with FAM, we make the following observations to conclude that it is unlikely that the increased gastric pH will decrease the absorption of NAC.

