The doses to be tested for famotidine are 20 mg thrice daily, 40 mg thrice daily, 80 mg thrice daily and no famotidine. The doses to be tested for n-acetyl cysteine are 600 mg thrice daily, 1200 mg thrice daily and 1800 mg thrice daily. The dose combinations are labelled 1 through 12 and are zoned as illustrated in Figure 10. The first zone has the combination of the lowest dose of each drug. The second zone has the combination of the lowest dose of each drug with the middle dose of each drug. The dose escalation starts with the first zone and follows with the second zone and then each combination of doses in the zone next closest to the coordinate

[figure not shown]

Figure 10. Dose Combinations of N-Acetyl Cysteine and Famotidine

origin shown in figure 10. Combination doses in the same zone are tested simultaneously using block randomization to control the number of patients for each open dose. Some combinations doses may close, in which case blocked randomization is applied to the remaining open combination doses in the same zone. A modified “3+3” design¹⁷² will be used for the initial dose escalation.

To find acceptable dose levels any grade 3 or higher toxicity will be considered a dose-limiting toxicity (DLT). The modified “3+3” design proceeds as described below. Three patients receive dose level 1. Their responses determine the subsequent steps as described in the following decision rules.

- (1) If two patients (2/3) experience DLT, then we close dose level 1 and all larger doses to testing.
- (2) If no patient experiences DLT, then we designate dose level 1 as an admissible dose, and open doses in zone 2 for testing.
- (3) If only one of the first three patients (1/3) experiences DLT, then we assign three more patients to dose level 1. In this case, we assign up to six patients to this dose, and the following decision rules apply:
 - a. If only one of the six patients (1/6) experiences DLT, then we designate dose level 1 as an admissible dose, and open doses in zone 2 for testing.
 - b. If two of the six patients (2/6) experience DLT, then we designate dose level 1 as an admissible dose, and doses in zone 2 and higher are closed to testing.
 - c. If more than two of the six patients (>2/6) experience DLT, then we close dose level 1 to testing, and we also close doses in zone 2 and higher.

ii) Study Procedure

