The randomization process will be performed using the Randomization module within REDCAP®. This will be performed through use of the data entry form entitled, “COVID-19 Test Result and Drug Randomization Case Report Form.” If the subject has a Rapid Test Performed in the ED and a positive result is obtained prior to discharge, the Co-Investigator who enrolled the subject will be able to access this form and perform the randomization. Otherwise, the randomization will be performed by the PI. Due to the trial design as a Phase I trial, the number of subjects on any arm can vary from zero to six depending on any dose limiting toxicities that may occur. Also, a new zone in the trial will not be able to open until all subjects in the previous zone have completed the trial. Therefore, the randomization process will be dynamic which REDCap® is incapable of handling directly but is capable of handling indirectly in a two-step process as described below. Prior to the start up the trial, a randomization lookup table will be uploaded into REDCap®, which will be nothing more than an ordered table from one to one hundred. While this may seem trivial, it is utterly essential in order to harness the power of REDCap® for a dynamic randomization process. After an investigator has performed the randomization task in REDCap®, the randomization number will be returned from this table. The investigator will then be required to lookup manually the arm to which the subject has been randomized in a file called “Dynamic Randomization Lookup Table” which they will only find within the “File Repository” in REDCap®. An example of this file can be found in the Appendix below. This file will be created prior to the trial initiation by the Lead Statistical Investigator initially assuming three subjects for each trial arm. Anytime, a change is needed to the “Dynamic Randomization Lookup Table” due to a DLT, the PI will suspend the ability for anyone to enroll or randomize a subject through the “User Rights” feature of REDCap® which can be used to restrict access by role to data entry forms. Once a decision has been made about either expanding or closing a trial arm due to a

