Other adverse reactions that were reported in less than 1 % of subjects in clinical trials include: fever, abnormal weakness or lack of energy; fatigue; heart palpitations; elevated liver enzymes; vomiting; nausea; abdominal discomfort; decreased appetite; dry mouth; decreased platelet counts in your blood; swelling of the tissue around your eyes; rash; eye redness and irritation; difficulty breathing; muscle pain; joint pain; seizure; hallucinations; depression; anxiety; decreased interest in sexual intercourse; difficulty falling asleep; prolonged sleeping; dry skin; flushing; ringing in your ears; altered sense of taste; and difficulty in men with achieving erections capable of intercourse. The following have also been reported during post-approval use of famotidine: changes to your heart by effecting the rhythm in which it beats; jaundice; inflammation and possible damage to your liver; decreased levels of white blood cells, red blood cells or platelets which could be life threatening; allergic reaction which could be life-threatening; rapid swelling of soft tissues often involving tissue around the face, limbs or genitals; hives; muscle damage; muscle cramps; confusion; agitation; tingling, numbness, or burning sensation in the skin often involving hands, feet, arms, or legs; pneumonia; and rash and blistering which could be life threatening.

The main risks to N-Acetyl Cysteine include but are not limited to the following: allergic reaction which could be life threatening; rash; itching; nausea or vomiting.

ii) Total Planned Enrollment

Estimated Number of Subjects: 42

We estimate a sample size of around 42 subjects for a 3+3 dose escalation period of our parallel phase I/II trial design. Based on our simulation of the phase I period of the trial and an assumption that a drug limiting toxicity ranges between 5% and 8%, we found an 83% chance that between 27 and 33 subjects would be required. During the adaptive phase of our trial with predicted rates of hospitalization ranging from 20 to 5% as shown in

iii) Does this study involve any of the following: prisoners, pregnant women, children, institutionalized individuals, or other populations that may be considered vulnerable?

No

iv) Does this study seek to exclude a specific racial, ethnic, or gender group? Include a compelling rationale if so.

No

v) Sources of Materials

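### The stated 83% chance that phase I needs 27–33 subjects cannot hold for the 12-arm design, where 33 or fewer has a probability of at most 26% (5% DLT rate) to 51% (8%)

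*Combined protocol and SAP*

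**What the plan says.** All references are to the combined protocol and SAP.

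- **Section IV) ii), Total Planned Enrollment.** The planned size is given as "We estimate a sample size of around 42 subjects for a 3+3 dose escalation period of our parallel phase I/II trial design". The next sentence assumes a DLT rate of 5% to 8% and reports, from a simulation of the phase I period, that "we found an 83% chance that between 27 and 33 subjects would be required". A further sentence, on the adaptive phase, breaks off in the available copy.
- **Section III) i), Phase I Portion.** Four famotidine levels (none, 20, 40 and 80 mg) are crossed with three NAC levels (600, 1200 and 1800 mg). "The dose combinations are labelled 1 through 12 and are zoned as illustrated in Figure 10".
- **Section II) i) b) 11, on absorption of NAC.** The same count appears as "twelve possible combinations described in greater detail below. Three arms are with NAC alone".
- **Section III) ii), Study Procedure.** The randomization lookup table is built "initially assuming three subjects for each trial arm", and "the number of subjects on any arm can vary from zero to six depending on any dose limiting toxicities that may occur".

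**The concern.** Twelve arms at three subjects each is 36, which is above the top of the range said to have an 83% chance. A total of 33 or fewer can occur only if toxicity stops escalation and at least one arm never opens. With DLT rates of 5% to 8%, that should be the less usual course of the trial.

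This is the only operating characteristic given for the escalation phase in the readable text. Taken at face value, it says that 42 leaves 42 − 33 = 9 to 42 − 27 = 15 subjects in hand. With a median of 39 the usual margin is 42 − 39 = 3, and an overrun is a real possibility. The IRB and DSMB, who may restrict or close arms, should have figures for the trial that will be run.

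**Working it through.** **Inputs.** 12 arms; three subjects per arm, with three more if exactly one of the first three has a DLT; DLT rate p of 5% or 8%. A stopping result is at least 2 DLTs in the first 3, or at least 2 in 6 after expansion (decision rules 1, 3b and 3c). Assumptions: 3/3 is treated like 2/3, which the rules do not list; DLTs are independent between subjects; an opened arm completes its cohort of three.

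**Step 1: probabilities per arm.**

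- Expansion: e = 3p(1−p)². At 5%, 3 × 0.05 × 0.9025 = 0.1354. At 8%, 3 × 0.08 × 0.8464 = 0.2031.
- Stopping result: q = 3p²(1−p) + p³ + e × [1 − (1−p)³].
  - At 5%: 0.0073 + 0.1354 × 0.1426 = 0.0266.
  - At 8%: 0.0182 + 0.2031 × 0.2213 = 0.0631.

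**Step 2: an upper bound that needs no zone map.** If all 12 arms open, N is at least 36. So N ≤ 33 requires an unopened arm, and hence a stopping result in at least one of at most 11 arms tested earlier:

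P(N ≤ 33) ≤ 1 − (1 − q)¹¹

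- 5%: 1 − 0.9734¹¹ = 25.6%
- 8%: 1 − 0.9369¹¹ = 51.2%

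This covers every total of 33 or fewer, not only 27–33, and does not depend on which arms a stop closes. For the bound to reach 83%, q would have to be 0.149, which needs a DLT rate of about 13.1%, outside the stated range.

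**Step 3: simulation on assumed zone maps.** Figure 10 is not shown, so several 12-arm layouts were tried: diagonal zones; a diagonal 3 × 3 grid with the NAC-alone arms placed in various zones; and square zones. Each was run with a stop closing all higher zones, and with a stop closing only larger doses.

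| Quantity | DLT 5% | DLT 8% |
|---|---|---|
| P(27–33) | about 1–9% | about 3–16% |
| P(N < 36) | about 12–21% | about 24–43% |
| P(36–42) | about 65–73% | about 38–52% |
| P(N > 42) | about 13–16% | about 18–28% |
| Median | 39 | 39 |

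On the plain diagonal map with whole-zone closure at 8%, the median lies on the border between 36 and 39. If no stop closes another arm, P(27–33) is 0.

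**Step 4: can the plan's figure be reproduced?** Not with 12 arms. It nearly can with nine, the 3 × 3 grid without the NAC-alone arms. There 27 = 9 × 3 and 33 = 27 + 2 × 3, so the range means at most two expansions. With closures ignored, the binomial probability of at most two expansions in nine arms is 88.9% at 5%, 81.3% at 6.5% and 73.0% at 8%. It averages about 81% over 5–8% and equals 83% near 6.2%. With closures counted on a diagonal nine-arm map it falls to 78–80% at 5% and 57–61% at 8%.

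**Step 5: the planned 42.** For 12 arms, 36 + 2 × 3 = 42. The mean without closures is 36 + 36e, which is 40.9 at 5% and 43.3 at 8%. With closures the simulated mean is lower, about 32 to 39.

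**The case against.** - **Arms may end with no subjects, so 36 is not a floor.** That is correct. A reader might infer that fewer than 36 is impossible, but the Study Procedure section allows zero-subject arms. The bound and the simulations both count them.
- **Figure 10 and part of the sizing paragraph are missing.** This limits the simulated ranges, which depend on the assumed zones; square zones with whole-zone closure give about 1% at a DLT rate of 5%. It would be wrong to read a precise probability of 27–33 into them. The bound uses neither item, and the 83% sentence is complete.
- **The range may describe only the nine true combinations.** Adding three NAC-alone arms of three gives 33 + 9 = 42, which would make the paragraph coherent. The match is close enough that an outdated or unlabelled figure is more likely than a faulty simulation. But the text speaks of the phase I period as a whole and nowhere limits the range to nine arms. Nor do the documents establish that the figure comes from an earlier nine-arm design; that remains an inference.
- **Little depends on the sentence.** This stands in part. No stopping rule, dose assignment or analysis uses 27–33, and enrollment need not change. That limits the consequence but does not make the figure right.

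**Conclusion.** Wrong as written. For the 12-arm design, P(N ≤ 33) is at most 25.6% at a 5% DLT rate and 51.2% at 8%, so 83% for the narrower range of 27–33 cannot be correct at the stated rates. This conclusion rests on 12 arms, cohorts of three, the stated decision rules and independent DLTs, but not on the zone map. The further figures (27–33 in roughly 1–16% of trials, a median of about 39, more than 42 in about 13–16% or 18–28%) do depend on assumed maps and should be replaced by the sponsor's own results.

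A reader might infer that the trial is wrongly sized. The documents do not support that: 42 equals 36 plus two expansions and lies between the two no-closure means. Those means ignore closures, and closures lower the expected total, so they give no ground for raising the target.

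**What to change.** Rerun the phase I simulation on all 12 combinations, with the actual zone map and the closure rules that will be applied. Replace the sentence giving 83% for 27–33 with the results at 5% and at 8%: the median, the chance of fewer than 36 (some arm unopened through toxicity), the chance of 36–42, and the chance of more than 42. Keep the planned total of around 42. If the sponsor finds that 27–33 was meant for the nine famotidine-plus-NAC combinations only, it may be kept under that label, with a statement of whether closures were counted, beside the 12-arm results.

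The cost is one rerun of an existing simulation and one replaced sentence. Enrollment and procedures do not change.

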Subjects will be contacted weekly at minimum by the assigned Research Assistant and the assigned Investigator. It will be the responsibility of the assigned Investigator to ensure this happens correctly. Depending how a subject is doing clinically, an Investigator will have the discretion to perform more frequent contacts. These contacts will preferably be done with both a video and audio connection for which the Vivify® devices are capable. A telephonic contact will be discouraged but will be permissible for those who do not have a Vivify® device or for whom an acceptable audio-video connection cannot otherwise be established. Data will be collected and recorded for these contacts on the appropriate REDCap® form, i.e., Research Assistant Weekly Assessment, or Investigator Weekly Assessment. It will be the responsibility of the assigned Research Assistant to enter weekly data from the patient's medication log and daily diaries into the REDCap® forms, Daily Medication Log and Daily Diary. If any new medications are started or any non-trial medications are changed by either the Investigator or any other provider involved in the subject's care as documented in EPIC, the Research Investigator will document such changes using the REDCap® form, New Medications. At the end of every evaluation by the assigned Investigator, the Investigator will document in the REDCap® form their assessment which must be one of the following: 1, Continue on Study Without Change; 2, Have made arrangements for short interval follow-up with myself; 3, Discontinue Study; 4, Recommend Evaluation in ER; 5, Recommend Evaluation by Primary Provider; 6, Recommend Dose Reduction in one or both Trial Medications. If the Investigator Documents any assessment other than "Continue on Study Without Change", an electronic notification will immediately be sent to the PI notifying the PI of the Investigator's Assessment. If the Investigator's assessment is to recommend a dose reduction, they will be directed to document such on the REDCap® form, Trial Drug Adjustment. Within this form, the new dosages will be documented, to include the possibility of discontinuing either or both medications. Additionally, the Investigator will be required to identify whether the adjustment is being made due to a drug toxicity. If the Investigator documents that the adjustment is made due to a drug toxicity upon saving the form an immediate electronic notification will be made to the PI and Chair of the DSMB. The PI will then complete the REDCap form "NCI Adverse Event Serious Adverse Event CTCAE v5." This is an extensive form for which the PI will complete for any AE or SAE. It is comprehensive as it includes the entirety of the CTCAE v5 to include every possible grade of toxicity. Through branching logic, it minimizes the task of data entry only to the particular organ systems or laboratory values involved, an allows the PI to easily document all the data necessary for AE and SAE determination so that the IRB, DSMB and FDA can all be notified as necessary and within the required timelines as described more fully in the "Protection Against Risk" section below.

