- Complications from procedures or a surgery
- Psychological, economic, or social harm

Causality Determination

All AEs will be assessed by either the sponsor-investigator and a determination of causality will be made as described below. Causality refers to the likelihood and extent that the investigational drugs being studied contributed to the development of an AE. Because the determination of causality involves medical decision making, only investigators as described above who have medical expertise will be making the causality or relationship determination. Any determination of causality will be reviewed by the Sponsor-Investigator and the Data and Safety Monitoring Board. If it is determined that an AE is related to the investigational drugs, required reporting to the IRB and FDA will be made in accordance with the required regulations.

When determining causality, the investigator will consider:

- Elimination of other causes
- Effect of the drug or drug class
- Temporal sequence
- Chronic effects
- Cumulative effects
- Late effects
- Re-challenge

Causality categories will include the following:

- ***Definitely related:*** There is a certainty that the event is related to the investigational product.
- ***Probably related:*** There is high likelihood that the event is related to the investigational product.
- ***Possibly related:*** There is a likelihood that the investigational product is the cause of the event, but other causes cannot be ruled out.
- ***Unlikely to be related:*** It is not likely that the event is related to the investigational product, and other more likely causes are present.
- ***Unrelated:*** Evidence exists that the event is related to something other than the investigational product.

Criteria for determining the causality category will be made as described in the below table.

Determination of Causality Category of AEs as Related to the Investigational Drugs	
Definite (must have all four [4])	
 1. Has a reasonable temporal relationship to the investigational drugs 2. Could not have readily been produced by the subject's clinical state or have been due to environmental or other interventions 3. Follows a known pattern of response to the investigational drugs 4. Disappears or decreases with reduction in dose or cessation of study drugs and recurs with re-exposure

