Probable (must have three [3])	
 1. Has a reasonable temporal relationship to the investigational drugs 2. Could not have readily been produced by the subject's clinical state or have been due to environmental or other interventions 3. Follows a known pattern of response to the investigational drugs 4. Disappears or decreases with reduction in dose or cessation of study drugs and recurs with re-exposure
Possible (must have two [2])	
 1. Has a reasonable temporal relationship to the investigational drugs 2. Could not have readily been produced by the subject's clinical state or have been due to environmental or other interventions 3. Follows a known pattern of response to the investigational drugs 4. Disappears or decreases with reduction in dose or cessation of study drugs and recurs with re-exposure
Unlikely (must	
 1. Does not have a temporal relationship to the investigational drugs

have two [2])	
 2. Could readily have been produced by the subject's clinical state 3. Could have been due to environmental or other interventions 4. Does not follow a known pattern of response to the investigational drugs 5. Does not reappear or worsen with reintroduction of investigational drugs
--------------------------	---

Duration of AEs

Another important element for evaluation of an AE is the duration of the event. Onset of the event will be measured from the onset of signs and symptoms. Resolution of the event will be recorded as well, which we will define as the point when all signs and symptoms have subsided.

Some events continue or change in severity over time. Capturing this information is also important. Changes in severity such as when an event improves from severe to mild will be recorded as separate events, with separate intensities and durations collected. The ongoing nature of the event will be noted in the subject's research record.

Determining Severity

An important component in evaluating AEs is their severity. Severity refers to the intensity of the event and will be indicated as mild, moderate, or severe, as shown in the table below.

Grading of Severity of AEs Based on Signs and Symptoms	
None	No signs/symptoms or within normal limits
Mild	Minor signs/symptoms; no specific medical intervention required; asymptomatic laboratory findings only, radiographic findings only; marginal clinical relevance

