These latter events, if serious, will still be reported to the IRB. Because all SAEs are still adverse events, they will be recorded on a Form FDA 3500A, which is the MedWatch Mandatory Reporting form.

Sponsor-Investigator's Responsibilities:

The Sponsor-Investigator will report SAEs that are unexpected and associated with the use of the investigational drugs to the US FDA within specific time periods. This report is an Investigational New Drug (IND) Safety Report. The objective of rapid notification is to protect subjects participating in this trial of the investigational drugs.

Unexpected adverse event or suspected adverse reaction refers to an event or reaction that is not listed in the investigator's brochure or is not listed at the specificity or severity that has been observed; or, if an investigator's brochure is not required or available, is not consistent with the risk information described in the general investigational plan or elsewhere in the current IND application.

- **Initial reporting:** The sponsor-investigator will report any suspected adverse reaction or adverse reaction to study treatment that is both serious and unexpected.

Unexpected fatal or life-threatening suspected adverse reactions represent especially important safety information and will be reported to FDA as soon as possible but no later than 7 calendar days following the sponsor-investigator's initial receipt of the information.

- **Follow-up reporting:** Any relevant additional information obtained by the sponsor-investigator that pertains to a previously submitted IND safety report will be submitted as a Follow-up IND Safety Report. Such report will be submitted without delay, as soon as the information is available but no later than 15 calendar days after the sponsor-investigator receives the information.

All IND safety reports will be submitted on Form FDA 3500A and will be accompanied by Form FDA 1571. The type of report (initial or follow-up) will be checked in the respective boxes on Forms 3500A and 1571.

The submission will be identified as:

- “IND safety report” for 15-day reports, or
- “7-day IND safety report” for unexpected fatal or life-threatening suspected adverse reaction reports, or
- “Follow-up IND safety report” for follow-up information.

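### The causality table credits improvement on stopping drug only if the event also recurs on re-exposure, so an unfamiliar event that COVID-19 could explain scores Unlikely even when it resolves off drug

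*Combined protocol and SAP*

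**What the plan says.** All references are to the combined protocol and SAP. Section V) ii) Protection against Risk, under Causality Determination, first defines the categories in words. Possibly related reads: "There is a likelihood that the investigational product is the cause of the event, but other causes cannot be ruled out". It then says that the category is determined by the criteria in a table. Definite needs all four criteria, Probable three and Possible two. In paraphrase, the criteria are (1) plausible timing, (2) not readily explained by the subject's condition or by other influences, (3) a known pattern of response, and (4) "Disappears or decreases with reduction in dose or cessation of study drugs and recurs with re-exposure". Unlikely needs two from a separate list of five, which includes an event the clinical state could readily have produced and one that "Does not follow a known pattern of response to the investigational drugs".

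On changes in dosing, section III) iv) e. (Outpatient Follow-up Data Collection Process) describes the Trial Drug Adjustment form: "Within this form, the new dosages will be documented, to include the possibility of discontinuing either or both medications". Section III) ii) (Study Procedure) has subjects stop study drug if hospitalized. Re-exposure is named as a factor to consider in Causality Determination and as reintroduction in the Unlikely row. Nothing says whether, when or how it would happen.

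On reporting to FDA, section V) ii) states: "The sponsor-investigator will report any suspected adverse reaction or adverse reaction to study treatment that is both serious and unexpected".

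**The concern.** Criterion 4 joins two facts with an and. The trial is set up to observe the first, improvement when the dose is lowered or stopped. It has no described route to the second, recurrence on re-exposure. Requiring both even in the Possible row means that improvement off drug, which the trial will often record, does not count.

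This bears on a particular kind of event. Every treated subject has SARS-CoV-2 infection, so criterion 2 will often fail. An effect not previously seen with either drug fails criterion 3. For an event that fails both, criterion 4 is the only remaining route from 1 point to the 2 needed for Possible. Safety is the primary outcome (section I), and section II) says the combination has not been studied in these outpatients. New toxicity is therefore what the relatedness summary most needs to show.

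**Working it through.** No stated sample size, power or error rate is involved. The check applies the table as a scoring rule.

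**Rule.** Score S = C1 + C2 + C3 + C4, each 0 or 1. S = 4 gives Definite, 3 Probable, 2 Possible. Score U counts the five Unlikely items, and U of 2 or more gives Unlikely. As written, C4 = 1 only if the event improved and also recurred on re-exposure.

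**Worked event.** Timing is plausible, COVID-19 could explain it, it is not a known pattern, there is no environmental or other cause, and there is no re-exposure.
- S = 1 + 0 + 0 + 0 = 1, below the 2 needed for Possible.
- U = 0 (timing) + 1 (clinical state) + 0 (environment) + 1 (no known pattern) + 0 (no reintroduction) = 2, so Unlikely is met.
- If the event improved on stopping, C4 is still 0, so S = 1 and U = 2 again. Improvement adds nothing.

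**Neighbouring events** (plausible timing, no environmental cause, no re-exposure), with the result after the change proposed under the fix:

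| COVID-19 could explain | Known pattern | S as written, improved or not | U | Result as written | If improved, after the change |
|---|---|---|---|---|---|
| yes | no | 1 | 2 | Unlikely | Possible row 2, U = 2: Possible, given a precedence rule |
| yes | yes | 2 | 1 | Possible | Possible row 3, Probable row 2: Possible |
| no | no | 2 | 1 | Possible | Possible row 3, Probable row 2: Possible |
| no | yes | 3 | 0 | Probable | Probable row 3: Probable |

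Of these four, the problem is confined to the first row: the event must be both explainable by COVID-19 and unfamiliar.

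**Why the change needs two parts.** Counting improvement alone lifts the worked event to 2 of 4, but it still scores 2 of 5 on Unlikely. It then meets both categories, and the table has no tie rule. The same tie already exists as written for an event with plausible timing and a known pattern that both COVID-19 and another intervention could explain: S = 1 + 0 + 1 + 0 = 2 and U = 0 + 1 + 1 + 0 + 0 = 2.

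**Table against definition.** The definition of Possibly related expressly allows for other causes that cannot be excluded. The worked event can fit it, yet the table returns Unlikely. The plan does not say which prevails, beyond stating that the table's criteria determine the category.

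**The case against.** The strongest reply has four parts.

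First, the worked event also fits the protocol's definition of Unlikely, which speaks of other, more probable causes. That stands. A reader might infer that the table's answer is simply wrong, but the documents show only that the table and the Possibly related definition can disagree.

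Second, attribution is a medical judgement. Causality Determination says so, and any determination is reviewed by the Sponsor-Investigator and the DSMB. This also stands, so the table does not wholly bind the outcome, although no rule is stated for departing from it. The adverse event form is not reproduced in the text available, so how causality is entered on it could not be checked.

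Third, the consequences are limited. A reader might infer that toxicities would be lost from the 3+3 count and unsafe zones opened. Section III) i) defines a dose-limiting toxicity as any toxicity of grade 3 or higher and sets no causality category, so there is no basis for putting a figure on that. A reader might also infer that Unlikely events are exempt from FDA reporting. Section V) ii) does relax expedited reporting for events not reasonably related to the drugs, but nothing equates that phrase with a table category. Adverse events are captured whatever their cause, and all serious ones go to the IRB within 24 hours.

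Fourth, requiring recurrence is a defensible strict standard in a self-limiting illness, particularly since section III) ii) normally stops the drugs once symptoms have improved. This has force for Definite and Probable. That Definite is out of reach without re-exposure is therefore not counted here as a defect. It has less force for Possible, the category meant to tolerate competing explanations.

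**Conclusion.** The point holds as a defect in the wording of one table. Read literally, and assuming no re-exposure takes place, improvement on reducing or stopping drug earns no credit in any row. An event with plausible timing that COVID-19 could explain and that is not a known pattern scores 1 of 4 and meets Unlikely with 2 of 5. This can conflict with the protocol's own definition of Possibly related.

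The likely effect is a relatedness summary, for the primary safety outcome, that understates possible involvement of the drugs in unfamiliar events. The category may also influence whether a serious unexpected event is regarded as a suspected reaction for FDA reporting, but that link is an inference and is not stated in the plan. How many events would be affected cannot be estimated from the documents. IRB reporting of serious events, capture of adverse events and the dose-limiting toxicity rule are untouched.

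**What to change.** In the Possible row, reduce criterion 4 to its first half, improvement when the dose is lowered or the drug stopped, and read the threshold as at least two criteria. Score it from the Trial Drug Adjustment form together with the recorded course of the event, counting only improvement dated after the adjustment. Under Duration of AEs a change in severity is logged as a separate event, so the records must be linked. Keep recurrence on re-exposure in criterion 4 for Definite, and for Probable unless the sponsor decides otherwise. State that an event meeting Possible is not downgraded to Unlikely, and reconcile the table with the category definitions in Causality Determination. No rule on whether to re-expose a subject is proposed.

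The cost is a wording change to one table and, if needed, to the adverse event form, with no new visits or data. The downside is that some COVID-19 symptoms that resolve by themselves after the drug is stopped will be classed Possible. The precedence rule could also lift an event with implausible timing: one that improved off drug, follows a known pattern and could be explained by COVID-19 would score 0 + 0 + 1 + 1 = 2. The sponsor may wish to limit the rule to events that meet criterion 1.
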